11.3 Populations for Analyses

The Intent to Treat (ITT) population consists of all patients who signed the written informed consent and are considered to meet all inclusion/exclusion criteria (patients included in the study) following the Intention To Treat principle whether patients have or not a procedure with one of the Integra or Codman External Ventricular Drainage System.

The Full Analysis Set (FAS) population consists of all patients included in the study who have a procedure with one of the Integra or Codman External Ventricular Drainage System. The primary endpoint and all other endpoints analyses will be based on the FAS population.

The Per Protocol Set (PPS) population consists of all patients who have a procedure with one of the Integra or Codman External Ventricular Drainage System and meet all inclusion/exclusion criteria. Endpoints analyses based on the PPS population will be supportive.

11.4 Statistical Analyses

11.4.1 General Approach

Descriptive statistics will be presented (e.g., number of observations, percentage, mean with standard deviation, median, range). Individual patient summaries will be tabulated in data listings. All observed data will be included.

Descriptive summaries will be the basis of study reports to generate an overall summary of the population characteristics and outcomes. Continuous outcome variables will be presented as means and standard deviations, as well as medians and ranges as appropriate. For categorical outcome variables, counts and percentages of subjects by category will be provided. Descriptive tables will be produced where applicable.

Statistical analyses will be performed using SAS/STAT software, Version 9.4 or higher of the SAS System for Windows.

Additional details on the analysis as well as any changes from the analysis plans presented in the protocol are provided in the Statistical Analysis Plan (SAP).

11.4.2 Measures to Minimize Bias

Potential for bias during this registry has been minimized by a well-controlled design, expected conduct under the terms of an approved clinical investigation plan and prospectively defined methods of data analysis. All patients meeting the criteria will have all available data relevant to the registry objectives collected. No blinding/masking will be conducted. Any known or foreseeable factors that may compromise the outcome of the registry study or the interpretation of results have been accounted for by the design of the registry study.

11.4.3 Analysis of the Primary Endpoint

The primary endpoint of this registry is the anticipated drainage (i.e., observed drainage consistent with the patient's clinical presentation) of cerebrospinal fluid (CSF) in the clinical setting until the EVD System is no longer required.

The number and percentage of patients with anticipated drainage (i.e., observed drainage consistent with the patient's clinical presentation) of cerebrospinal fluid (CSF) in the clinical setting until the EVD System is no longer required will be presented. The primary hypothesis will be tested using the exact (Clopper-

Pearson) method along with two-sided 95% confidence interval. The primary objective will be met if the lower bound of the 95% confidence interval is greater than the performance goal of 80%.

11.4.4 Analysis of the Secondary Endpoint

The secondary endpoint is the proportion of patients in whom the CODMAN Cranial Access Kit, when used with appropriate accessories, provided successful access to the intracranial space. The number and percentage of patients with intracranial space success, along with two-sided 95% confidence interval of the percentage will be provided.

11.4.5 Analysis of the Tertiary Endpoints

The tertiary endpoints include:

- Number of initial Catheter Insertion Attempts [Time Frame: Implantation of subject] Number of insertions needed to place initial Catheter
- Number of days initial Catheter is in place.
- Number of Catheter and/or EVD System replacements during treatment, if applicable.
- Number of Catheter flushing interventions per each Catheter if a replacement Catheter is implanted.
- Length of Catheter Tunneling into the Brain [Time Frame: Implant of subject] Length of tunneling of EVD Catheter in the brain for each analysis population.
- Number of Days with initial Indwelling Catheter [Time Frame: Implant of subjects to the day of explant] Days Catheter was implanted in subjects
- Non-infectious Catheter Failure in the intent-to-treat (ITT) Population [Time Frame: Implant of subject to explant] Reasons for non-infectious Catheter malfunctions in the ITT population.
- CSF daily drainage

Descriptive statistics will be provided to summarize the secondary endpoints. Continuous outcome variables will be presented as means, standard deviations, medians, and ranges as appropriate. For categorical outcome variables, counts and percentages of subjects by category will be provided along with 95% confidence interval of the percentage.

11.4.6 Safety Analyses

The safety endpoints of this study are:

- Device- or procedure-related adverse events (AEs) during the use of the device in the patient
- Noted Device Deficiencies during use of the device such as malfunction, use errors, or other issues related to the performance or safety of the External Ventricular Drainage Systems and Accessories

AEs will be coded using the MedDRA terminology for data summaries. Each AE will be coded with 2 levels including Preferred Term (PT) and System Organ Class (SOC).

The total number of EVD system and accessories-related AEs as well as the percentage of patients with at least one device-related AE will be presented overall and by SOC and PT. AEs will also be tabulated by severity and by relationship to EVD system or accessories within each SOC and PT. A listing of EVD system and accessories-related AEs and SAEs will be presented respectively.

The total number of DDs as well as the percentage of patients with at least one DD will be presented overall and by drainage system. A listing of DDs will be presented.

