5.4. Safety Endpoints

The safety endpoints include:

1. Device- or procedure related adverse events (AEs) during the use of the device in the patient
2. Noted Device Deficiencies during use of the device such as malfunction, use errors, or other issues related to the performance or safety of the External Ventricular Drainage Systems and Accessories.

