8.10.1. Adverse Events

All AEs and complications occurring from the time of subject enrollment until study termination or study completion include intra-operative AEs and complications. AEs will be coded using the Medical Dictionary for Regulatory Activities (MedDRA) terminology for data summaries. Each AE will be coded with 2 levels including Preferred Term (PT) and System Organ Class (SOC). The severity of all adverse events will be reviewed and adjudicated and classified as mild, moderate or severe.

The total number of device-related AEs as well as the percentage of patients with at least one device-related AE will be presented overall and by SOC and PT. AEs will also be tabulated by severity and by relationship to device within each SOC and PT. A listing of device-related AEs and SAEs will be presented respectively.

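### Safety endpoint 1 covers device- or procedure-related adverse events, but the only related-event count and patient percentage planned are for device-related events

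*Protocol*

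**What the plan says.** The endpoint is stated the same way wherever it appears. Protocol 3.6 and 11.4.6 give it as "Device- or procedure-related adverse events (AEs) during the use of the device in the patient", and SAP 5.4 as "Device- or procedure related adverse events (AEs) during the use of the device in the patient". The schedules of activities in both documents also list procedure-related events among the safety data to be collected.

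Protocol 11.4.6 then names the outputs:

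- a count and a patient percentage: "The total number of EVD system and accessories-related AEs as well as the percentage of patients with at least one device-related AE"
- a table: "AEs will also be tabulated by severity and by relationship to EVD system or accessories within each SOC and PT"
- a listing: "A listing of EVD system and accessories-related AEs and SAEs will be presented respectively"

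SAP 8.10.1 plans the same three for the device: "The total number of device-related AEs as well as the percentage of patients with at least one device-related AE", "AEs will also be tabulated by severity and by relationship to device within each SOC and PT" and "A listing of device-related AEs and SAEs will be presented respectively". SAP 8.10 puts all safety summaries on the full analysis set (FAS) and plans no formal test.

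Protocol 9.3 says that the sponsor and investigators will separate device-related from procedure-related events, and that one event can be both.

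**The concern.** The endpoint has two arms joined by *or*. The planned count and percentage estimate only the device arm. An event judged related to the placement procedure but not to the device belongs to the endpoint as defined, yet has no place in the planned rate. The omission can move the reported percentage in one direction only, towards a more favourable safety result.

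The excluded arm is clinically relevant. The protocol synopsis describes infection and hemorrhage as the commonest complications of these procedures and gives pediatric hemorrhage rates of 10% at placement and 21.9% at removal. Those figures say nothing about how such events would be attributed, so they show relevance and not the size of the gap.

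The other safety endpoint shows the contrast: for device deficiencies, Protocol 11.4.6 plans a count, a patient percentage and a listing that match the definition.

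A secondary difficulty lies in Protocol 9.3, which does not use the word procedures in one sense throughout. Two sites could classify the same placement bleed differently, and each could cite 9.3.

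**Working it through.** The plan gives no figure to reproduce. The check is a comparison of endpoint and outputs, followed by simple arithmetic for the size.

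**Step 1. Each planned output against the endpoint.**

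| Output (same in both documents) | Events covered | Relationship used | Combined endpoint readable? |
|---|---|---|---|
| Event count | Related events only | Device | No |
| Patient percentage | Related events only | Device | No |
| Table by severity and relationship | Adverse events in general | Device | No: procedure-related events may appear, but not labelled as such |
| Listing | Device-related events; the SAE part may be read as all SAEs | Device | No: a listing gives no rate, and non-serious procedure-only events are absent |

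No output in Protocol 11.4.6 or SAP 8.10.1 gives a count or percentage for procedure-related events or for the combined endpoint.

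**Step 2. Direction and size.** Let D be the FAS patients with at least one device-related event, P those with at least one procedure-related event, and N the FAS size.

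- Endpoint as stated: |D ∪ P| / N
- Percentage as planned: |D| / N
- Difference: |P not in D| / N = k / N, which is never negative

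Here k is the number of FAS patients whose related events are all procedure-related and not device-related. The documents do not give k, and it may be 0.

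The FAS size is assumed to lie between the calculated sample size of 110 and the planned enrolment of 120 (Protocol 11.2). The two agree with the stated 8% drop-out: 120 × (1 − 0.08) = 110.4, about 110.

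- N = 120: 1/120 = 0.83 percentage points for each such patient
- N = 110: 1/110 = 0.91 percentage points for each such patient

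**Step 3. What procedure means.** Step 2 depends on the sense of the word.

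- *Broad sense.* One of the criteria in Protocol 9.3 for ruling out relatedness refers to the procedures by which the device is applied. Protocol 8.3, the second note to 9.1.2, and 9.4 (which speaks of the surgery) fit that sense. Placement complications are then in P, and the difference is k/N.
- *Literal sense.* The paragraph in 9.3 on separating device from procedure limits procedures to those peculiar to the registry, and treats complications of routine procedures that the plan does not impose as unrelated. Protocol 2.3 and 4.4 say that the registry adds nothing to standard of care. P is then empty and the difference is 0, but only because half of the endpoint has been defined away.

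**Step 4. Whether the data will exist.** Protocol 9.3 requires the distinction and both schedules collect procedure-related events. The causality item in 9.7 names only the investigational product. The data capture system itself is not in the documents, so a separate field for relationship to procedure can be neither assumed nor ruled out.

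**The case against.** The strongest case on the other side has four parts.

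1. *Nothing is lost.* Protocol 9.7 collects all adverse events whatever their relatedness, SAP 8.10.1 includes intra-operative events and complications, and SAP 8.1 promises tables and listings of all data, with the number and percentage for each category of a categorical variable. This stands as far as it goes. A reader might infer that procedure-related events vanish from the report; the documents do not support that, because the severity and relationship table is not restricted to device-related events and the SAE part of the listing can be read as all SAEs. But a general clause names no combined rate, and none of the listed outputs supplies one.

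2. *The procedure-only group may be very small.* Protocol 9.1.1 counts events from inadequate implantation or operation, and from use error, as adverse device effects. The cranial access kit, hand drill and drill bit are themselves registry products (Appendix 14.3). Drill-hole bleeding appears under anticipated device effects (9.4.1), and cases that cannot be assessed default to possible (9.3). All of this stands, and it is why no value of k is offered.

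3. *The conflict in 9.3 is loose wording.* The broad phrase is one criterion and not a definition, and the sentence on routine procedures follows a mention of diagnostic and patient-management procedures, so it need not reach implantation. Most readers would probably adopt the broad sense. That makes the wording a secondary matter. It also confirms that the sense most readers would take is the one under which the planned rate is incomplete.

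4. *Nothing turns on the rate.* Safety is descriptive and untested. That is correct and limits the weight of the point.

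**Conclusion.** The point holds as an inconsistency between a stated endpoint and its analysis. Followed as written, the plan never estimates safety endpoint 1; it estimates the device arm only. On the broad sense of procedure, the reported percentage is equal to or lower than the endpoint by k/N: 0.83 to 0.91 percentage points per affected patient for N from 120 to 110, with k unknown and possibly 0. The direction is certain on that reading. The size cannot be derived from the documents.

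Three stronger inferences are not supported. A reader might conclude that the safety rate will be materially understated, but no procedure-only share is given. A reader might conclude that the data capture system lacks a field for relationship to procedure, but 9.7 leaves this open while 9.3 and the schedules point the other way. And a reader might treat this percentage as what decides the safety objective, but the objective is only to capture safety data, device deficiencies stand beside it as the second safety endpoint, and no decision rule or test uses either.

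It should be corrected before the final analysis, because the change is cheap and the present wording can err only in the favourable direction.

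**What to change.** *Main change, Protocol 11.4.6 and SAP 8.10.1.* Report the number of events and the percentage of FAS patients with at least one event related to the device or the procedure, in total and by system organ class and preferred term. Follow with the device-related and procedure-related components separately, noting that an event can count in both. Add a listing that matches the combined endpoint, and state whether its SAE part covers all SAEs or only related ones.

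*Secondary, Protocol 9.3.* Reconcile the restriction to registry-specific procedures with the broader use elsewhere in 9.3 and in 8.3, 9.1.2 and 9.4, so that one definition covers the procedures by which the device is applied. State that the sentence on routine procedures does not reach them.

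*Secondary, Protocol 9.7.* Confirm that relationship to procedure is recorded separately from relationship to device, as 9.3 requires, and say so.

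*Cost.* Protocol and SAP wording, a few table rows and one listing. Only if the procedure relationship proves not to be recorded would a field be needed, with re-assessment of events already entered. Sample size and significance level are unaffected. The reported rate will be the same or less favourable.

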11.4.7 Baseline Descriptive Statistics

The baseline patient characteristics will be summarized using descriptive statistics (continuous outcome variables will be summarized using means and standard deviations, as well as medians and ranges; categorical outcome variables will be summarized by presenting the number and percentage of subjects in each category).

A patient listing of this data will also be provided.

Other data pertinent to the EVD System and Accessories or relevant patient care may be summarized.

11.4.8 Planned Interim Analysis

There are no planned interim analyses.

11.4.9 Sub-Group Analyses

Subgroup analyses will be performed for drainage systems for primary endpoint and secondary endpoint. The purpose of the subgroup analysis is not to reach statistically significant results within each subgroup, but rather to assess the consistency and robustness of the treatment effects across the subgroups. Descriptive statistics will be used for the subgroup analysis. Two-sided 95% confidence intervals will be reported as appropriate for reference purpose only. No multiplicity adjustment will be considered for the subgroup analysis.

EVD Systems:

- AccuDrain
- Hermetic Plus
- LimiTorr
- MoniTorr
- Codman EDS 3 / EDS 3C
- Basic CSF Drainage System
- External Ventricular Drainage System

11.4.10 Tabulation of Individual Participant Data

Individual patient data will be listed by measure and time point where appropriate.

11.4.11 Exploratory Analyses

Any exploratory analyses will be pre-specified in the SAP.

11.4.12 Missing Data

Analysis of performance and safety data will be primarily performed on all observed (available) data. No imputation methods on missing data will be performed. Based on the primary point, missing data is expected to be minimal. Reasonable efforts will be made to obtain complete data for all subjects. If despite these efforts, missing data occurs, reasons for missing data will be summarized, including withdrawal of consent.

12 SUPPORTING DOCUMENTATION AND OPERATIONAL CONSIDERATIONS

12.1 Regulatory, Ethical, and Study Oversight Considerations

12.1.1 Informed Consent Process

12.1.1.1 Consent/Accent and Other Informational Documents Provided to Participants

Consent forms will be EC-approved, where applicable, and the participant or their legally authorized representative will be asked to read and review the document and provide written authorization via signature to participate in the registry study.

12.1.1.2 Vulnerable population

Patients will be receiving CSF Drainage as part of standard of care and no additional risks or procedures will be conducted outside of standard of care.

There may be situations where patients are treated with the External Ventricular Drainage Systems, but where the patients are not able to provide informed consent for data collection prior to treatment. This may be the case in situations such as, but not limited to, post-traumatic hydrocephalus, post-hemorrhagic stroke, or intracranial tumor. These situations are expected to happen relatively frequently, and data referring to the use of the device in these situations are considered of value for the evaluation of clinical safety and performance of the device.

However, for these patients, their willingness to volunteer in data collection for the purposes of the registry study cannot be confirmed, and these patients thus meet the criteria of vulnerable population as defined in ISO 14155, Section 3.55. Therefore, in these cases, informed consent may be obtained by the patient's legal authorized representative.

12.1.1.3 Consent Procedures and Documentation

Non-vulnerable population

Patients must be fully counseled and informed of their options, risks and benefits, and should have every opportunity to ask questions about participation in the registry study. This process includes a thorough explanation of the patient information letter and informed consent form that the patient will be asked to sign acknowledging that they understand and desire to participate in the registry study.

The investigator is responsible for assuring that written informed consent is obtained from each patient prior to participation in the registry study. Should the investigator delegate the responsibility of

conducting the informed consent process to a designee, the investigator must ensure and document appropriate training of the authorized designee.

The investigator will use an EC approved informed consent form, where applicable, that was prepared in accordance with this clinical investigation plan, ISO 14155 and regulatory requirements.

Informed consent must always be obtained from a patient prior to initiation of any data collection dictated by the clinical investigation plan. A copy of the signed and dated statement of informed consent, as well as any other written information, will be provided to the patient.

If new information regarding the investigational device becomes available and/or the clinical investigation plan changes and this information can significantly affect a patient's future health and medical care, patients will be informed of the information and may be asked to sign a revised informed consent form.

Vulnerable population

Patients' legally authorized representative must be fully counseled and informed of the options, risks and benefits, and should have every opportunity to ask questions about participation in the clinical investigation. This process includes a thorough explanation of the patient information letter and informed consent form that the legally authorized representative will be asked to sign acknowledging that they understand the requirements of participation in the clinical investigation.

The investigator is responsible for assuring that written informed consent is obtained from each legally authorized representative prior to participation in the clinical investigation. Should the investigator delegate the responsibility of conducting the informed consent process to a designee, the investigator must ensure and document appropriate training of the authorized designee.

The investigator will use an EC approved informed consent form that was prepared in accordance with this clinical investigation plan, ISO 14155 and regulatory requirements.

Informed consent must always be obtained from the legally authorized representative prior to initiation of any data collection dictated by the clinical investigation plan. A copy of the signed and dated statement of informed consent, as well as any other written information, will be provided to the patient and the legally authorized representative.

If new information regarding the investigational device becomes available and/or the clinical investigation plan changes and this information can significantly affect a patient's future health and medical care, patients and their legally authorized representative will be informed of the information and may be asked to sign a revised informed consent form.

